In May 2013, the Board of Directors of the International Society for the Study of Women's Sexual Health (ISSWSH) and the Board of Trustees of The North American Menopause Society (NAMS) endorsed the term genitourinary syndrome of menopause (GSM). This term encompasses the numerous changes that occur as a result of the decrease in estrogen and other sex steroids, including vaginal atrophy and sexual dysfunction [1]. In a cross-sectional study of US postmenopausal women, those with sexual dysfunction were 4 times more likely to have vulvovaginal atrophy [2]. With the rising elderly population, the impact of VVA and sexual dysfunction on quality of life and health care costs is a growing issue. In 2000, there were 26.25 million women over the age of 60 years old, and this number is expected to almost double by the year 2030 [3]. Currently VVA affects up to 60% of postmenopausal women, and its most common

Updated 11/27/17

Pg. 1

symptom is dyspareunia [4,5]. Further, if left untreated, it can increase rates of infection, and negatively impact a woman's sexual health and quality of life [6]. While only 25% of women with VVA seek medical advice, only 3% of women reveal problems with sexual health without being prompted [7,8].

There are several established methods of treatment for VVA. Vaginal estrogen is considered the treatment of choice. While several studies have shown that vaginal estrogen does not increase serum estrogen levels above postmenopausal values, there is still significant controversy surrounding the use of estrogen and the risk of breast cancer and uterine cancer [9,10]. This study is important because we hope to prove a non-estrogen medication to be an effective non-hormonal alternative therapy for vulvovaginal atrophy.

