Specific Aim 2: *To compare the effects of ospemifene and vaginal conjugated estrogens on symptoms of VVA.* We hypothesize that treatment with either ospemifene or vaginal conjugated

estrogens will demonstrate comparable improvements in VVA symptoms. In the population randomly treated with vaginal conjugated estrogens or ospemifene in specific aim 1, we will compare the change from baseline and between groups.

Significance

Female Sexual Dysfunction

Traditionally, female sexual dysfunction (FSD) is defined as the disorder of desire, arousal, pain and/or muted orgasm in women [28]. While many people may consider this disorder to be pertinent only during reproductive years, it is very common in the menopausal women population, affecting 57% of women in menopause [5]. In 2014, Nappi et al published a review of data that shows the importance of discussing sexual function and vaginal atrophy with postmenopausal women. 1 in 5 women over the age of 70 still engage in intercourse. Moreover, 71% of women agree that, "it was important to them to maintain an active sex life." The article also adds that only 3% of women will seek advice about sexual function if not prompted. Many who do bring this problem to their provider's attention feel as though it is dismissed. Meanwhile, providers tended not to proactively address sexual health for middle and later life-aged women, because of time constraints, inadequate training, personal attitudes and beliefs that sex is not a priority for older patients [29].

What is Vulvovaginal Atrophy?

There is significant overlap between FSD and VVA. Women with FSD are almost 4 times as likely to have VVA [29]. Once a woman reaches menopause, her ovarian production of estrogen decreases dramatically. The vagina and vulva are two organs that are affected by the lack of estradiol in the body. Without estrogen, the vagina epithelial cells decline in maturation, and there is also an increase in the vaginal pH. These changes lead to the common symptoms of painful intercourse, vaginal dryness, pain, and itching. They also put the vaginal epithelium at risk for infection and inflammation. Further, the increase in pH is associated with an increased rate of recurrent urinary tract infections in postmenopausal women [13]. In the US, approximately 60% of women report symptoms related to vulvovaginal atrophy [4].

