Once a qualifying subject is identified, she will be randomized into a treatment group. The participant will be randomized to receive either a vaginal conjugated estrogens prescription or an ospemifene prescription. A computerized randomization program will be used to perform block randomization in random blocks of 4 and 10. Allocations envelopes containing the assignment will be used for the study. They will be sealed opaque envelopes with aluminum foil inside. They will also contain carbon-copy paper. The treatment number will be printed on the envelope. Once the participant has signed the informed consent form, her name will be printed on the envelope, which will transfer over to the carbon-copy paper, and the envelope will be opened.

Study Plan

The patient will be informed of her assigned medication, and she will receive a medication coupon to help offset the cost of the medication. Each medication is FDA-approved for long-term use of at least 52 weeks. For this study, a 12-week prescription for the medication will be sent electron-

[figure not shown]
ically to the pharmacy of her choice. Treatment with estrogen will consist of 0.5 gram of conjugated estrogens placed vaginally for 12 weeks. Treatment with ospemifene will consist of a 60mg tablet that will be taken at the same time daily for 12 weeks.

The patient will receive an intake packet that includes the following information:

1. Copy of signed informed consent form
2. Important contacts and instructions for emergency/adverse events
3. Allocation card
4. Medication's FDA packet insert
5. Instructions on dosing
6. 12-week date to repeat questionnaires

She will be called the following day to confirm her start date of the medication. They will return at 12 weeks and complete the same FSFI and Likert Scale questionnaires regarding sexual function and VVA symptoms. The questionnaires may also be completed over the phone with the investigator.

Alternatively, if time during clinic is limited, the patient can be consented and allocated to a medication in person, by a co-investigator. She will be called by a co-investigator on the same day to complete the enrollment and questionnaires. Below is a summary of the study plan.

Sample Size Analysis

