To our knowledge, there has been no prior study that reported the prevalence of female sexual dysfunction amongst women using vaginal conjugated estrogens, defined as having an FSFI score of 26.55 or less. With an FSD prevalence of 57%, we determine a 50% reduction in the prevalence to be clinically significant. Setting an alpha of 0.05, and a power of 0.80, and assuming a minimum of 15% dropout rate, the sample size is set to 52 in each group.

Specific Aims

Specific Aim 1: To compare the efficacy of each drug in improving sexual function.

- a. Experimental Design: In this study, participants will be asked to complete the 19-question female sexual function index (FSFI) questionnaire at the beginning of the study period and at 12 weeks. The results will be used to compare the effect of each medication on the various domains of sexual function.

The mean total score in each treatment group at baseline will be compared using Student's t-test. Additionally, the score of the components of desire, arousal, lubrication, orgasm, satisfaction and pain will be similarly compared. Later, the change in these scores between the two treatment groups at 12 weeks will be compared using a paired t-test analysis.

Anticipated Results and Interpretation: We expect to see similar results in this study, showing comparable improvements in vaginal lubrication and dyspareunia, while showing greater improvement for overall sexual health in the ospemifene group.

Potential Pitfalls, Alternative Approaches, and Future Directions: We do not anticipate any challenges with the administration and analysis of this questionnaire.

Specific Aim 2: To compare each drug's impact on VVA symptoms

- a. Experimental Design: Participants will complete a Likert scale of symptom severity at the beginning and at the end of the study. The symptoms listed will include dyspareunia, vaginal dryness, vaginal pain, and vaginal itching. The survey will ask them to rate the severity of each VVA symptom on a scale of 0 to 3, with 0 being none, 1 being mild, 2 being moderate, and 3 being severe. It will also ask them to choose their most bothersome symptom (MBS).

The mean score of the MBS in each treatment group at baseline will be compared using Student's t-test. Later, the change in score of the MBS between the two treatment groups at four weeks and again at 12 weeks will be compared using a paired t-test analysis.

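### Aim 2 plans a change-from-baseline comparison and names a paired t-test; run literally this is a within-arm test, which two open-label active arms cannot interpret as drug effect

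*Combined protocol and SAP*

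**What the plan says.** The first Specific Aims section states, for Aim 2, that "we will compare the change from baseline and between groups". Its hypothesis is that treatment with either drug or "estrogens will demonstrate comparable improvements in VVA symptoms".

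The second Specific Aims section, after Sample Size Analysis, gives the experimental design. Four symptoms are rated "on a scale of 0 to 3, with 0 being none, 1 being mild, 2 being moderate, and 3 being severe". Of the survey it says: "It will also ask them to choose their most bothersome symptom (MBS". The quantity analysed is "the change in score of the MBS between the two treatment groups at four weeks and again at 12 weeks", and it "will be compared using a paired t-test analysis". Aim 1 names the same test for the change in FSFI scores between the groups.

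Randomization and Allocation Concealment gives two active arms and no other: "The participant will be randomized to receive either a vaginal conjugated estrogens prescription or an ospemifene prescription". The Overview under Approach says that neither participants nor clinicians can be blinded. The Introduction says "we hope to prove a non-estrogen medication to be an effective non-hormonal alternative therapy for vulvovaginal atrophy".

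**The concern.** Women in two randomised arms are not paired with one another. The only natural pairing in these data is a woman's baseline score with her own follow-up score. A paired t-test applied as written is therefore a test of change within an arm, and the Aim 2 wording, which lists change from baseline next to the between-group comparison, points the same way.

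This design cannot attribute such a change to a drug. The outcome is self-rated, treatment is open label, and no placebo or untreated arm shows how far scores would fall anyway. The tracked score may also be subject to selection: a symptom picked because it is troublesome at one visit tends to score lower at the next. Because the hypothesis expects improvement on both drugs, significant falls in both arms could be taken as confirming it when neither drug had contributed. If an analyst follows the named test, the randomised comparison, which is the part protected from these effects, may not be the one carried out.

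**Working it through.** **Inputs from the documents.** 52 per arm, alpha 0.05, power 0.80, 15% dropout, and a prevalence of sexual dysfunction falling from 57% by half to 28.5% (Sample Size Analysis); four symptoms scored 0 to 3 (Aim 2); dyspareunia required at entry, with no minimum score (Table 1).

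**Assumptions.** The documents give no SD of change, retest reliability or non-specific response. Two-sided testing, retest reliability of 0.5 to 0.9, and the score distributions and inter-symptom correlations used in the simulations are all assumed.

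**1. The plan's own figure.** Two proportions, unpooled variance:

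n = (1.96 + 0.84)² × (0.57 × 0.43 + 0.285 × 0.715) / 0.285² = 43.4, rounded up to 44. Then 44 / 0.85 = 51.8, rounded up to 52.

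The stated size is reproduced. It rests on prevalence of sexual dysfunction, so it says nothing about the symptom analysis, but it does give about 44 evaluable women per arm.

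**2. How small a non-drug change becomes significant.** For a paired t-test the noncentrality is δ√n, where δ is the mean change divided by the SD of change. By the noncentral t distribution:

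| Evaluable per arm | δ for 50% | δ for 80% | δ for 90% |
|---|---|---|---|
| 44 | 0.30 | 0.43 | 0.50 |
| 52 | 0.28 | 0.40 | 0.46 |

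If the SD of change is 0.8 points (assumed), a non-drug fall of 0.30 × 0.8 = 0.24 points is declared significant half the time with 44 women.

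**3. Zero-effect simulation.** Neither drug does anything. The table gives the chance that a within-arm paired t-test shows significant improvement in a given arm of 44, as assumed reliability rises from 0.5 to 0.9.

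| How the tracked symptom arises | Significant improvement |
|---|---|
| Fixed at baseline, highest score that day | 99% down to 69%; 60% to 73% at reliability 0.9 under other cut points and symptom correlations |
| Fixed at baseline, only loosely tied to that day's score | 81% down to 36% |
| Dyspareunia dominant at baseline, highest score | 86% down to 40% |
| Dyspareunia dominant at baseline, loosely tied | 60% down to 25% |
| Always dyspareunia, score of at least 1 at entry | 19% down to 8% |
| Stable true worst symptom | about 2.5% to 3% |
| Re-chosen at each visit as that visit's highest score | about 2% to 3%; 2% to 9% if dyspareunia must score at least 1 at entry |

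A two-sided 5% test with no bias gives 2.5% in the direction of improvement, so the stable-worst row and the lower figures of the re-chosen row show essentially no distortion. In the first row, letting measurement errors correlate across symptoms lowers the range to 45% to 89%.

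**4. Adding non-specific response.** With an assumed 0.2-point improvement in everyone, at reliability 0.7 and 0.9, the rates become over 99% (highest score), about 96% (loosely tied) and 67% to 77% (dyspareunia only). This mechanism does not depend on how the symptom is chosen.

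**5. The randomised comparison.** In the zero-effect simulations, an independent-samples comparison of change between arms is significant in 4.4% to 6.0% of trials, against a nominal 5%. Regression to the mean and non-specific change enter both arms alike and cancel on average.

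**The case against.** The strongest reply is that the plan never specifies a within-arm test of the most bothersome symptom. The sentence listing change from baseline is an overview of symptoms in general and names no test. The experimental design, where the most bothersome symptom appears, describes a comparison between the two groups. On that view the paired t-test is a misnamed test. This is a fair reading, and the between-arm comparison is indeed planned and unaffected by these mechanisms. What remains is that the named test does not perform that comparison, and if run as named it performs the other one.

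A reader might go further and infer that the trial would usually show significant improvement on either drug even if neither worked. The documents do not support this. They do not say that the tracked symptom is fixed at baseline: the survey containing the question is completed at the start and at the end. Nor is most bothersome the same as highest scored; it is the woman's own choice, and since every participant has dyspareunia it may often be that symptom.

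A reader might also infer that within-arm change is the only support for calling ospemifene effective. It is not: the Ospemifene section cites earlier placebo-controlled trials, and the Introduction later frames the aim as efficacy relative to vaginal estrogen. The plan nowhere says that a within-arm fall will be reported as proof of efficacy, and its hope in the Introduction is background wording that needs no statistical correction.

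Finally, choosing a most bothersome symptom has no bearing on Aim 1, because the FSFI involves no such choice.

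**Conclusion.** The point holds as a defect in the stated analysis: a change-from-baseline comparison is listed, the named test would carry it out, and the design cannot interpret the result as drug effect. That conclusion needs no simulation; it follows from two open-label active arms with no untreated arm.

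The size is not settled by the documents. False improvement in roughly 60% to 99% of trials requires a symptom fixed at baseline that follows the highest score that day, with retest reliability of 0.5 to 0.9 and independent measurement errors. About 2% to 3% applies if the symptom is re-chosen at each visit or is the stable worst one, before any non-specific response. It would be wrong to quote only the upper range.

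The correction is worth making whichever applies, because it uses data already collected. Aim 1 shares the misnamed test but not the selection issue.

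**What to change.** In both Specific Aims sections, define the Aim 2 analysis as the between-arm difference in the 12-week symptom score, adjusted for baseline score by ANCOVA, with its 95% confidence interval, in place of the paired t-test. Treat any four-week comparison that is kept in the same way.

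State that the tracked symptom is the one each woman chooses at baseline and that this symptom is scored at follow-up. This keeps the same symptom under comparison over time. It may bring regression to the mean into each arm's change, but that cancels between randomised arms.

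Report within-arm changes descriptively, with a sentence saying that they are not evidence of efficacy.

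Replace the paired t-test in Aim 1 by the same baseline-adjusted comparison, because it too is named there for a comparison between arms.

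The cost is wording. No extra participants, visits or data are needed, and the trial gives up only a within-arm efficacy claim that it could not support. The corrected analysis estimates one drug relative to the other; it does not show that either works against no treatment.

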In 2013, Ospemifene was approved by the Food and Drug Administration for the treatment of moderate to severe dyspareunia that is due to menopause [10]. Ospemifene is a non-estrogen selective estrogen receptor modulator (SERM). SERMs are estrogen receptor (ER) agonist/antagonists that typically induce the desirable effects of estrogen while avoiding estrogen-related adverse effects. Unlike other drugs in this class, Ospemifene has been shown to have significant estrogenic agonist effects on the vagina and bone, but antagonist effects on breast tissue [6]. Furthermore, it significantly improves overall sexual function [12]. Despite this promising medical profile, it remains a second or third line of therapy to treat VVA. More research is needed to determine if ospemifene is an acceptable, and possibly a favorable, alternative to vaginal estrogen for the treatment of vulvovaginal atrophy, especially if there is any concern for sexual function. In this research study, we aspire to determine the efficacy of ospemifene compared to a vaginal estrogen. The primary aim of this research is to compare female sexual function as measured by a validated instrument in women randomized to receive ospemifene and vaginal estrogen. Secondary aims include comparing markers of vaginal health and safety in both treatment groups.

Hypothesis

Ospemifene is a nonhormonal alternative that has proven to significantly improve sexual health and vulvovaginal atrophy, yet vaginal estrogen is still considered the first-line therapy. Our null hypothesis is that ospemifene has a similar efficacy as vaginal conjugated estrogens for improving sexual function in postmenopausal women who have vulvovaginal atrophy.

Specific Aims

Specific Aim 1: *To compare the efficacy of ospemifene and vaginal conjugated estrogens on female sexual function.* Ospemifene is the only non-estrogen that is FDA-approved to treat dyspareunia in postmenopausal women. Further, studies report a significant improvement in sexual health in patients that are treated with ospemifene [12]. However, vaginal estrogen therapy (with conjugated equine estrogen or estradiol) remains the most commonly prescribed treatment for dyspareunia. To our knowledge, a direct comparison of ospemifene and local vaginal estrogen therapy on postmenopausal female sexual function has not been performed. We hypothesize that ospemifene provides a greater improvement in sexual function in postmenopausal women with dyspareunia and VVA.

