In essence, Ospemifene seems to be a possible wonder drug for menopausal women. While it's primary use is for VVA-associated dyspareunia, there is consistent evidence of protective activity in bone and breast tissue, while showing no evidence of carcinogenic potential in the endometrium, breast, or liver. Similar to vaginal estrogen, ospemifene has not been studied longer than 12 months to determine long term risks of the medication [6]. Appendix 1 shows a summary of adverse events in various safety studies for vaginal estrogen and ospemifene. Research is

promising that Ospemifene may prove to be a safer and more beneficial choice for all postmenopausal women, regardless of their history of breast or endometrial cancer.

Innovation

Several studies have published data regarding the unique behavior of ospemifene in postmenopausal women. Nonetheless, vaginal estrogen is still seen as the gold standard for the treatment of VVA, regardless of the woman's most bothersome symptom. To our knowledge, for the first time, this study will directly compare the efficacy of vaginal conjugated estrogens and ospemifene in improving sexual function in postmenopausal women who have vulvovaginal atrophy. By also directly comparing symptom improvement with VVA treatment, this study hopes to answer the question of whether or not clinicians should shift towards ospemifene as a first line treatment for sexual dysfunction in postmenopausal women with VVA.

Approach

Overview

This study will be a prospective, randomized study that will compare efficacy and safety of ospemifene and vaginal estrogen. Because of the route of administration for each drug, it is not possible to blind the participants or clinicians to the treatment. However, we will be collecting objective data that cannot be misinterpreted by those collecting and analyzing the data. We hope to effectively inform clinicians who treat postmenopausal women that suffer from VVA about the efficacy of ospemifene as it compares to vaginal conjugated estrogens cream. As a specialty with a high population of patients who complain of VVA, we are very familiar with this patient population, as well as the use of vaginal estrogen in their treatment. This puts this research team in an ideal position to properly execute the study and interpret the findings.

Patient Groups

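### The protocol offers objective data as its safeguard for an open-label design, but every efficacy outcome it describes is self-reported, and some may be given by phone to an investigator for whom no masking is described

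*Combined protocol and SAP*

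**What the plan says.** **Blinding.** The Overview under Approach states that "it is not possible to blind the participants or clinicians to the treatment". The next sentence is the only safeguard offered: "However, we will be collecting objective data that cannot be misinterpreted by those collecting and analyzing the data". Under Study Plan, "The patient will be informed of her assigned medication".

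**Efficacy outcomes.** Under Specific Aim 1 (after Sample Size Analysis), participants "complete the 19-question female sexual function index (FSFI) questionnaire at the beginning of the study period and at 12 weeks". Under Specific Aim 2, "Participants will complete a Likert scale of symptom severity at the beginning and at the end of the study". "The survey will ask them to rate the severity of each VVA symptom on a scale of 0 to 3", and each woman also picks her most bothersome symptom. At 12 weeks, Study Plan schedules these two questionnaires and nothing else.

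**Mode of collection.** The default at week 12 is a return visit, but "The questionnaires may also be completed over the phone with the investigator". In the alternative pathway, used when clinic time is short, the woman is consented and allocated in person. A co-investigator then phones her the same day for the baseline questionnaires.

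**Other hints of objective measurement.** The Introduction says "Secondary aims include comparing markers of vaginal health and safety in both treatment groups", and the anticipated results of Aim 2 mention objective findings in passing. Neither is tied to a measurement that is defined, scheduled or analysed.

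**The concern.** The safeguard sentence describes a property that the collected data lack. Sexual function and symptom severity as rated by the woman are legitimate outcomes, but they are subjective. When the treatment is known, the rating can be influenced by what she expects of the drug. Answering intimate questions aloud to a member of the study team can add to this, particularly as the Hypothesis and Specific Aim 1 sections state that the team expects ospemifene to do better on sexual function.

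The primary comparison is a between-arm difference in self-reported change. A difference in reporting between arms enters that comparison directly, and neither randomisation nor sample size removes it. The Innovation section says the trial should inform whether clinicians move to ospemifene as first-line treatment. If the sentence stands, the report could present its result as protected from bias when the design does not provide that protection.

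**Working it through.** **1. Which outcomes are objective?**

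| Outcome | Source of the value | Drug known at week 12? |
|---|---|---|
| FSFI total and six domains | woman's answers | yes |
| FSFI of 26.55 or less (basis of the sample size) | derived from the same answers | yes |
| 0-3 rating of four symptoms | woman's rating | yes |
| Most bothersome symptom | woman's choice and rating | yes |

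No pH, maturation index, examination or other measured marker appears in the text of Patient Groups, Study Plan or either Specific Aim. The Study Plan figure was not available for this check. The text around it schedules only questionnaires at 12 weeks.

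**2. Who takes the answers?** No masked interviewer, assessor or analyst is described. The text does not require the same mode at baseline and week 12, or in both arms. In the alternative pathway, baseline follows allocation. In the default pathway, Patient Groups places the forms after enrolment, and the randomisation section opens the envelope after consent. The order of those two steps is not fixed.

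**3. Evaluable number per arm.** This starts from the plan's own sample size. Inputs from Sample Size Analysis are 57% reduced by half to 28.5%, alpha 0.05 (two-sided assumed), power 0.80 and 15% dropout. With the unpooled two-proportion formula:

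n = (1.960 + 0.842)² × (0.57×0.43 + 0.285×0.715) / 0.285² = 7.849 × 0.4489 / 0.0812 = 43.4, so 44.

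44 / 0.85 = 51.8, so 52. The stated 52 per group is reproduced, and 44 is the evaluable number used below.

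**4. What a reporting bias would do.** The documents give neither an SD for FSFI change nor any bias, so both are assumptions and are shown over a range. With no true difference and bias b:

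SE = SD × √(2/44)

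P(significant) = Φ(b/SE − 1.960) + Φ(−b/SE − 1.960)

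Example with SD 6 and b = 2: SE = 6 × 0.2132 = 1.279 and b/SE = 1.563. Then Φ(−0.397) + Φ(−3.523) = 0.346 + 0.000, about 35%.

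| SD of change | SE | b = 1 | b = 2 | b = 3 |
|---|---|---|---|---|
| 6 | 1.28 | 12% | 35% | 65% |
| 8 | 1.71 | 9% | 22% | 42% |
| 10 | 2.13 | 8% | 16% | 29% |

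With b = 0 every row gives 5%. A larger trial would not help: SE falls as n rises, so a fixed bias becomes more likely to reach significance.

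**The case against.** **The sentence is about collectors and analysts, not participants.** This is partly right. Fixed-response items on a validated questionnaire leave little room for interpretation at scoring. A reader might infer that the plan has no protection at all, and that goes too far. What stands is that this protection does not make the data objective, does not cover what a woman who knows her drug reports, and weakens when answers are given aloud.

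**Open label is unavoidable here, and sexual function has to be self-reported.** Both points are accepted, and neither design choice is criticised. The problem is the assurance attached to them and the avoidable interviewer step.

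**Phone completion is optional, and the caller's knowledge of allocation is not stated.** This is correct. That the caller is unmasked is inferred from the Overview and from the absence of any masking provision. Nothing suggests that phone use would differ between arms. The protocol also does not say that visit forms are self-completed.

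**Any bias need not favour ospemifene.** This is also correct. A reader might infer that bias would run in the hypothesised direction throughout. Aim 2 expects comparable symptom improvement, and Aim 1 expects comparable lubrication and dyspareunia, so a shift toward ospemifene would contradict those expectations. Women's expectations could go either way, since the protocol calls vaginal estrogen the standard treatment and also says many women avoid it.

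**The illustration assumes its inputs.** It does. It applies to one continuous FSFI score and should not be carried over to the 0-3 symptom item.

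**Conclusion.** The point holds. The Overview's assurance does not match the outcomes the protocol describes: all the efficacy measures are participant-reported under open treatment, and part of the collection may pass through an interviewer for whom no masking is described. This limits what the trial can conclude.

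The documents do not show that a bias will occur, how large it would be, or which arm it would favour. The figures (12%, 35% and 65% at SD 6; 8%, 16% and 29% at SD 10) show only how readily a modest reporting difference could produce a significant result. They rest on 44 evaluable women per arm, no true difference, a two-sided 5% test, and assumed SDs and biases.

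A reader might also infer from "Secondary aims include comparing markers of vaginal health and safety in both treatment groups" that a whole secondary aim cannot be answered. The documents do not support that. It is a loose phrase in the Introduction. The operative second aim, symptoms of vulvovaginal atrophy, is defined and can be answered, so this is a minor wording mismatch.

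**What to change.** 1. **Overview.** Replace the objective-data sentence with a statement that all efficacy outcomes are participant-reported and unblinded, so reporting bias cannot be excluded. Carry that limitation into the conclusion of the report.
2. **Study Plan.** Have the FSFI and symptom scale self-completed, on paper or electronically, in the same mode at baseline and week 12 and in both arms. Complete the baseline forms before the envelope is opened, in the alternative pathway too. Keep a scripted phone call only as a fallback against missing data, made where possible by an existing team member unaware of allocation. Record the mode used for each questionnaire.
3. **Introduction (minor).** Align the secondary-aim wording with what is measured, namely severity of vulvovaginal atrophy symptoms.

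**Cost.** No extra patient or procedure is needed. Some forms will come back late or not at all and will need reminders, which matters in a trial that already allows for 15% dropout. A masked caller may be hard to arrange, and a woman may reveal her drug during the call. The bias from women knowing their treatment remains after these changes, so it has to be acknowledged.
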